#### c.1.b Design of VERTPAC-02 study

This will be a phase II study of 15 (UCL) + 15 (Mayo) patients with histologically proven advanced or locally advanced PanCa or other solid tumors unsuitable for surgical resection. In the first 5+5 patients, EUS guided verteporfin PDT will be used with light delivered at just one site. In the following 10+10 patients, light will be delivered with the fiber at multiple positions, as required to ensure treatment of all appropriate areas of the cancer, as was done in the previous studies with percutaneous fiber insertion. Each patient will be given verteporfin 0.4 mg/kg bodyweight intravenously, followed by light activation 60 minutes after photosensitization (acceptable treatment window 60- 90 minutes). Light delivery will take place via a 5-20 mm length diffuser fiber placed under EUS guidance using red laser light at 690nm. The light dose delivered down the fiber will be fixed at 40 -80 J/cm, which was found to be optimum in our previous VERTPAC-01 study. All patients will be prescribed ciprofloxacin as a prophylactic to reduce the potential risk of infection associated with the fine needle puncture of the tumor. If a patient is allergic to ciprofloxacin, another acceptable broad spectrum antibiotic will be prescribed at the investigators discretion.

Patients will be evaluated by contrast enhanced CT at 2 days after PDT (treatment day 3), and they will be able to commence conventional palliative chemotherapy after that if they so wish within a week of PDT. Patients will also have additional blood draws taken for biomarker analysis before, during, and after their treatment. In previous studies, it was a protocol requirement that chemotherapy

not be given within a month of PDT. However, PDT is a local, one off treatment and chemotherapy is systemic and ongoing. It is an important innovation to give chemotherapy much earlier after PDT as our previous study on PDT for biliary tract cancer showed that delay in giving chemotherapy after PDT put patients at a disadvantage. Treatment response and time to disease progression will be assessed by CT scans at three-monthly intervals, as part of usual practice. Thereafter, patients will continue to be followed up for survival data. Second line chemotherapy and/or re-treatment with verteporfin PDT for progressive disease will be at the discretion of the investigators.

**c.1.c Patient eligibility:** See Table 1.

Inclusion Criteria	Exclusion Criteria
Histological/cytological Dx of advanced or locally advanced or small volume metastatic PanCa or other solid pancreatic tumor that is not amenable to curative surgical resection, or the patient is unfit, or declines surgery	For locally advanced patients, evidence of metastases other than lung or liver. For lung metastases, greater than three lesions and any lesions greater than 5cm are excluded. For advanced patients, any metastasis is acceptable for enrollment
Age > 18 years	Age < 18 yr; Porphyria; pregnant or breast-feeding
Measurable disease as defined by the Response Evaluation Criteria in Solid Tumors (RECIST)	Locally advanced disease involving > 50% circumference of the duodenum or a major artery within the treatment area
ECOG performance status 0, 1 or 2	ECOG performance status 3 or 4
Estimated life expectancy of at least 12 weeks	Previous treatment with curative intent for current disease within the past two weeks (i.e. prior resection, radical radiotherapy or chemotherapy)
Capable of giving written informed consent	Any psychiatric disorder making reliable informed consent impossible
Adequate biliary drainage (serum bilirubin < 2.5 ULN), with no evidence of active uncontrolled infection (patients on antibiotics are eligible)	A history of documented hemorrhagic diathesis or coagulopathy on therapeutic anticoagulation; History of prior or concomitant other malignancy that will interfere with the response evaluation
Women of child-bearing potential with a negative pregnancy test (qualitative serum HCG) prior to study entry AND must be using an adequate contraception method, which must be continued for 1 week after PDT	Any evidence of severe or uncontrolled systemic diseases or laboratory finding that in the view of the investigator makes it undesirable for the patient to participate in the trial
	Contrast allergy not amenable to treatment with steroids and antihistamines

### Sample Size and Power Calculation

We have previously shown that the above treatment parameters result in at least a 12 mm region of necrosis around percutaneously placed fibers in PanCa, which will be considered criteria for a positive response. If we observe 16 (out of 30) patients with a positive necrosis region response around at least one of the fibers inserted, this would indicate that the true response rate is at least 53% (with 90% power and assuming a 25% variance), which will be significantly higher than the known response rate of at most 30% for palliative chemotherapy (50).

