### Criteria for early termination of the trial

As in our previous trials in this application, a DSMB will monitor toxicity. A grade 3 or 4 toxicity rate of >30% would be considered unacceptable. Therefore, if  $\geq 13$  patients (out of 25) suffer a grade 3/4 toxic event, the DMEC would consider stopping the trial because the likelihood of this occurring by chance alone is 0.02 (statistically significant at the 5% level) if the true toxicity rate were  $\leq 30\%$ .

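### The 16-of-30 criterion has 56% power at a true response rate of 53%, not 90%, and 16 responders would not show a true rate of at least 53%

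*Combined protocol and SAP*

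**What the plan says.** In the combined protocol and SAP, section c.1.b sets the size of the study: "This will be a phase II study of 15 (UCL) + 15 (Mayo) patients". The section Sample Size and Power Calculation defines a positive response as at least 12 mm of necrosis. It then gives the criterion: "If we observe 16 (out of 30) patients with a positive necrosis region response around at least one of the fibers inserted". The inference to be drawn from such a result is put this way: "this would indicate that the true response rate is at least 53% (with 90% power and assuming a 25% variance". The sentence ends with the comparison, "which will be significantly higher than the known response rate of at most 30% for palliative chemotherapy", and cites reference 50, a paper tabulating exact one-stage phase II designs.

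The section states no alpha and no sidedness for efficacy, and does not say what follows from fewer than 16 responders. The only significance level nearby, "statistically significant at the 5% level", is in Criteria for early termination of the trial and belongs to the toxicity rule.

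**The concern.** The paragraph ties together a count (16 of 30), a true rate (53%) and a power (90%). These cannot all hold. The expected number of responders at a true rate of 53% is 30 × 0.53 = 15.9. A cut-off at the expected count is reached only a little more than half the time.

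The stated conclusion has a separate fault. Since 16/30 = 53.3%, the rate that the result is said to establish as a minimum is just the observed proportion, with no allowance for sampling error in 30 patients.

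This is the only power statement for the primary objective, and the Summary presents the trial as the step towards the later combination trial. The two risks are a worthwhile effect missed far more often than the text suggests, and a result of 16 reported as stronger than it is. A false positive against 30% is not the problem, because the rule is strict in that direction.

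**Working it through.** **Inputs.** n = 30 (section c.1.b and the sample size section); cut-off 16, reference rate 30%, true rate 53%, power 90% and variance 25% (all from the sample size section). Efficacy alpha is not stated, so several values are tried where it matters.

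**1. Can the stated 90% be reproduced?** Not for a cut-off of 16. The nearest route is a normal approximation that takes the 25% as the maximum binomial variance, 0.25:

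power = Φ[(p1 − p0)/√(0.25/n) − z]

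With p1 = 0.53: (0.53 − 0.30)/√(0.25/30) = 0.23/0.0913 = 2.52.

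- One-sided alpha 10%: Φ(2.52 − 1.28) = 89.2% (89.9% with p1 = 16/30)
- One-sided alpha 5%: Φ(2.52 − 1.645) = 80.9%
- One-sided alpha 2.5%: Φ(2.52 − 1.96) = 71.2%

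So about 90% appears only at a one-sided alpha of 10%, which the document never mentions. The critical proportion on that route is 0.30 + 1.28 × 0.0913 = 0.417, or 12.5 of 30. That is a cut-off of 13, not 16.

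**2. Exact power of the stated count.** With X binomial(30, p), power is P(X ≥ r | p = 0.53) and type I error is P(X ≥ r | p = 0.30).

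| Cut-off r | Type I error at 30% | Power at 53% | Power at 16/30 |
|---|---|---|---|
| 13 | 8.4% | 89.3% | 90.0% |
| 14 | 4.0% | 81.0% | 82.0% |
| 15 | 1.7% | 69.6% | 70.9% |
| 16 | 0.64% | 55.9% | 57.4% |

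Once the cut-off is fixed, power depends only on n, r and p, so no choice of alpha or sidedness alters the last row. Solving P(X ≥ 16 | p) = 0.80 and 0.90 for p gives true rates of 59% and 63%.

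**3. What 16 of 30 shows about the true rate.** The exact (Clopper-Pearson) lower limit is the α quantile of a Beta(x, n − x + 1) distribution, here Beta(16, 15). For the two-sided 95% interval α = 0.025. The last column is the smallest count whose lower limit reaches 53%.

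| Confidence level | Lower limit at 16/30 | Shortfall from 53% | Count needed |
|---|---|---|---|
| One-sided 90% | 40.1% | 12.9 points | 20 |
| One-sided 95% | 37.0% | 16.0 points | 21 |
| Two-sided 95% | 34.3% | 18.7 points | 22 |

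The full two-sided 95% interval is 34.3% to 71.7%. Equally, 16 or more responders would occur with probability 43% if the true rate were 50%, and 23% if it were 45%.

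**4. The comparison with 30%.** P(X ≥ 16 | p = 0.30) = 0.0064, and the two-sided 95% lower limit of 34.3% lies above 30%. This part of the sentence is correct.

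**The case against.** The best defence is that the paragraph does not set a success rule. It gives 16 of 30 as a result that might be observed, does not say 16 or more, and does not call 53% the design alternative. The 90% and the 25% variance could then describe the ability of 30 patients to detect 16/30 against 30%. On a one-sided 10% test that comes to 89.9% by the normal approximation and 90.0% by the exact rule of 13 or more. This would also explain the otherwise unexplained variance figure.

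As an account of where the 90% came from, this is plausible. It does not rescue the text. It needs an alpha the document does not give; at one-sided 5% or 2.5% the same approximation at 16/30 gives only about 82% or 72%. It also corresponds to a cut-off of 13, so the stated count and the stated power would come from different rules. Under a heading about sample size and power, a count followed by a conclusion and a power is most naturally read as the criterion, and the cited reference on exact designs points the same way.

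What does stand is that the 44% chance of missing a true rate of 53% applies only if fewer than 16 is treated as failure, which the sponsor should confirm. The error in the claim of at least 53% does not depend on this reading.

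**Conclusion.** The concern holds. With n = 30 and success at 16 or more responders, power at a true rate of 53% is 55.9% (57.4% at 16/30), against the stated 90%. The chance of missing such an effect is 44%, not 10%. The power result assumes that 16 or more is the success rule and 53% the alternative. Without that assumption, a result of 16/30 still does not establish a true rate of at least 53%: that wording exceeds the exact lower limit by 13 to 19 percentage points, depending on the confidence level. The claim that 16/30 is significantly above 30% stands. Nothing elsewhere in the document corrects the other two statements, so they should be corrected.

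**What to change.** Keep 30 patients and the count of 16, and replace the paragraph with wording such as:

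> The null response rate is 30%. With success defined as at least 16 of 30 responders, the exact one-sided type I error is 0.6%, and power is 56% at a true rate of 53%, 80% at 59% and 90% at 63%. The observed proportion will be reported with its exact confidence interval (at 16/30: 53%, two-sided 95% CI 34% to 72%).

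Delete the statement that the result would indicate a true rate of at least 53%, and the reference to a 25% variance, which exact figures do not need. The sponsor should confirm that 16 is meant as the success threshold, since this wording makes the rule explicit.

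The cost is one reworded paragraph and a less favourable stated power, with no extra patients.

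If about 90% power at 53% is wanted, the sponsor must first state alpha and sidedness. With 30 patients, a cut-off of 14 gives alpha 4.0% and power 81%, and a cut-off of 13 gives alpha 8.4% and power 89%. Exact designs for 30% against 53% with 90% power need 39 patients and a cut-off of 17 at one-sided 5%, or 47 patients and a cut-off of 21 at one-sided 2.5%. Any of these changes the design and would be a substantive amendment.

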### **Hypothesis 1: EUS-guided PDT will provide effective ablation of solid lesions of the pancreas (multi-center phase II clinical trial at UCL + Mayo).**

Clinical use of PDT for PanCa has been pioneered by the Project 2 group, and a positive correlation was established between delivered energy and the extent of tumor necrosis around interstitial fibers, with no serious adverse events. We aim to improve the approach by moving to a minimally invasive approach of EUS, in conjunction with dosimetry to monitor treatment (jointly with *Project 4*).

**Aim 1.** To participate in the conduct a phase II study of EUS-guided PDT in PanCa. PDT will be done initially at a single site with a fixed light dose for the first group of patients, then at multiple sites to match the zone of tumor necrosis to tumor volume.

This work will lead into the next logical step in the trial, which was the major goal of Project 2, namely a combination therapy trial using PDT, standard chemotherapy and in patients with advanced or locally advanced and metastatic disease. The advanced cancer patients will be defined as patients with at least a 50% increase in tumor volume or new metastasis regardless of whether the patients had chemotherapy. All participants will be within ECOG performance status of 0-2. This work provides a direct bench-to-bedside translation, as we will use the most effective combination sequence form project 3 as they study in pre-clinical work. While this is not the goal of this current supplement, it is a future direction, which will be expedited by the completion of this proposed Phase II trial.

After intravenous administration of verteporfin, fluorescence readings will be taken from the patient's buccal mucosa to register the fluorescence peak. This is performed using a mobile fluorimeter that uses an ipad as the processor. The device delivers a very small amount of light to the buccal mucosal and can measure nanogram levels of drugs. A gradient spectrophotometer is coupled to a CCD to record the fluorescence. Background fluorescence will be performed earlier in the day from the same area of buccal mucosa. The measurements will be taken every 10 minutes until the procedure (total 6-9 measurements).

We plan to take FNA biopsies of the lymphocytes to assess immune response due to treatment.

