#### **b.1 EUS-guided PDT will enable effective ablation of solid tumors of the pancreas.**

Based on our collaborators at the University College London's previous animal experimental work, and our pre-clinical and clinical trials of pancreatic PDT, a phase I study of verteporfin PDT in locally advanced unresectable PanCa (VERTPAC-01) was undertaken. In the initial dose escalation part of the study, patients were treated with verteporfin PDT to assess its general safety profile, to determine the optimum treatment parameters needed to achieve effective and safe necrosis of tumor, and to confirm safety of administration of subsequent conventional palliative chemotherapy. Inclusion criteria included a histopathological/cytological diagnosis of PanCa, unresectable, non-metastatic disease confirmed at multidisciplinary review and adequate biliary drainage (serum bilirubin < 2.5 x upper limit of normal). All patients received a dose of verteporfin 0.4 mg/kg bodyweight intravenously, followed by light activation 60 minutes later under subdued lighting conditions. Treatment was via a single 10 mm tip diffuser fiber which was placed under CT guidance by an experienced radiologist (Figure 1). With increasing light doses, there was an increase in the extent of tumor necrosis around the fiber with no serious adverse events or reports of photosensitivity. This study aims to replicate these findings using the minimally invasive approach of EUS. Initially, only a single position of the laser fiber will be used, but in later patients multiple fiber positions will be used to show that it is possible to treat the full volume of appropriate cancers with endoscopic placement of the treatment fiber in more than one site. This is essential to show that endoscopic fiber placement can cover a comparable volume of tumor to the multi-fiber, percutaneous approach used in the previous studies.

**Fig. 2. Patient undergoing verteporfin PDT.** The image on the left shows a baseline contrast-enhanced CT with a low attenuation mass in the head of the pancreas. The centre image shows percutaneous needle placement into the tumour. The image on the right shows the day 5 post PDT contrast-enhanced CT with a  $2.67 \text{ cm}^3$  zone of necrosis in the region of the pancreatic head.

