#### **c.1.h Treatment Evaluation**

##### **PRIMARY Response evaluation**

- Contrast-enhanced CT scans of the pancreas will be evaluated before treatment and on day 3 (after treatment on day 1), for measurement of tumor volume using RECIST criteria and to assess the extent of tumor necrosis after treatment.

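### Meeting 16/30 would show only that the 12 mm necrosis rate exceeds a chosen 30% floor; it would not show superiority to chemotherapy, a true rate of 53% or more, or 90% power at 53%.

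*Combined protocol and SAP*

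**What the plan says.** The Sample Size and Power Calculation section takes its response criterion from earlier work: "the above treatment parameters result in at least a 12 mm region of necrosis around percutaneously placed fibers in PanCa". A patient counts as a responder with a "positive necrosis region response around at least one of the fibers inserted". The section gives no rate for the earlier percutaneous result.

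It then draws two conclusions from 16 responders in 30. The first is that "this would indicate that the true response rate is at least 53% (with 90% power and assuming a 25% variance"). The second is the comparison with chemotherapy, "which will be significantly higher than the known response rate of at most 30% for palliative chemotherapy (50").

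The outcome is read early. Under PRIMARY Response evaluation (c.1.h), CT is read at baseline and again "on day 3 (after treatment on day 1), for measurement of tumor volume using RECIST criteria and to assess the extent of tumor necrosis". Section c.1.b places that CT two days after PDT and allows chemotherapy only afterwards. It assesses treatment response and time to progression separately, by three-monthly CT. All 30 patients receive PDT. The first 10 are treated at one fibre position. For the rest, "In the following 10+10 patients, light will be delivered with the fiber at multiple positions".

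**The concern.** The comparison sets two different outcomes side by side. One is a zone of necrosis around a fibre two days after light delivery. The other is called a response rate to palliative chemotherapy. A patient given chemotherapy alone has no fibre, so the 30% cannot be a rate of the first outcome.

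The documents do not close the gap. Section a.2 reports the chemotherapy trials by survival and gives no response rate. The only citation beside the 30% is bibliography item 50, by its title a paper of sample size tables for exact single-stage phase II designs.

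The sentence about 53% has a separate fault: it presents the observed proportion as a lower bound on the true rate and attaches a power figure to it.

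This is the only numerical efficacy rule for the primary objective. A reader who relied on it could credit the trial with a comparative finding, a minimum response rate and a power that it does not have.

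**Working it through.** **Inputs.** From the sample size section: n = 30, success if X ≥ 16, comparator rate 30%, claimed true rate 53%, claimed power 90%. No significance level or sidedness is stated for efficacy. X is the number of responders and is taken as binomial. All results are exact.

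**1. The plan's own figures.** 16/30 = 0.533, so the 53% is the observed proportion. Against a fixed 30%, P(X ≥ 16 | 0.30) = 0.0064 one-sided, so 16/30 does exclude 30% and that part holds. The stated power does not: P(X ≥ 16 | 0.53) = 0.559, and 0.574 at a true rate of exactly 16/30. A true rate equal to the cut-off proportion gives a little over an even chance of passing.

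**2. Rate needed for 90% power.** Solving P(X ≥ 16 | p) = 0.90 gives p = 0.630.

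**3. Could another cut-off give 90% at 53%?** With n = 30, X ≥ 13 gives power 0.893 at 53%, but P(X ≥ 13 | 0.30) = 0.084. An exact design for 30% against 53% with 90% power needs n = 39 at one-sided 5%, or n = 47 at one-sided 2.5%. The 90% therefore does not reproduce with n = 30 at either level.

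**4. What 16/30 supports as a minimum.** Clopper-Pearson limits:

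| Interval | Lower | Upper |
|---|---|---|
| Two-sided 95% | 34.3% | 71.7% |
| One-sided 95% | 37.0% | – |
| One-sided 90% | 40.1% | – |

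None of these lower limits is near 53%.

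**5. Dependence on the null.** One-sided P(X ≥ 16):

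| Null rate | P(X ≥ 16) |
|---|---|
| 30% | 0.0064 |
| 35% | 0.030 |
| 40% | 0.097 |
| 50% | 0.43 |

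The conclusion depends on where the floor is set, so the source of the 30% matters.

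**6. Comparison with chemotherapy.** Nothing can be computed. The documents give no rate of 12 mm necrosis without PDT.

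**7. What the pooled rate can hide.** 16/30 arises from 2/10 single-position plus 14/20 multi-position responders (20% and 70%), and equally from 6/10 plus 10/20 (60% and 50%).

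**The case against.** No objective, aim or response evaluation item tests superiority to chemotherapy. The primary objective (c.1.a) is effective direct ablation, and the comparison is one clause in the sample size paragraph. Read as a fixed floor, 30% works, and 16/30 excludes it. Reference 50 may have been cited for the design method and misplaced after the 30%. The earlier percutaneous response rate may be in a cited paper that is not available here. All of this stands, and it makes the repair mainly one of wording and stated operating characteristics. It does not rescue the clause, which calls the 30% chemotherapy's known rate and not a floor.

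Several stronger readings are tempting and are not supported:

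- *The trial will report superiority to chemotherapy, or carry that claim into the combination studies.* The documents contain no such reporting rule. Specific Aims says only that the results will inform later designs.
- *Pooling one-position and multi-position patients inflates type I error.* If every patient's chance of response is 30%, the error is 0.6% however many positions are used. That the criterion is easier to meet with several positions also needs an assumption about per-position success that the documents do not give.
- *The plan fails because tumour coverage has no success threshold.* Aim 1 says light will be delivered "then at multiple sites to match the zone of tumor necrosis to tumor volume", and section b.1 calls it "essential to show that endoscopic fiber placement can cover a comparable volume of tumor to the multi-fiber, percutaneous approach used in the previous studies". These state purpose and rationale, not a success criterion, and the CT measurements needed to describe coverage are already planned.
- *VERTPAC-01 used one fibre, so it cannot be the multi-fibre benchmark.* The single-fibre description in b.1 follows from its account of the dose-escalation part, and a later multi-fibre part is not excluded.

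**Conclusion.** The point holds in a limited form. Meeting 16/30 would show that the patient-level rate of 12 mm necrosis exceeds 30% (one-sided p = 0.0064), with a supported minimum of about 34% to 37% at 95% confidence. It would not show superiority to chemotherapy or a true rate of 53% or more. The 90% power is overstated by about 34 percentage points at 53% (90% − 56%).

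The outcome mismatch is an inference, because the endpoint behind the 30% is never defined. It is a firm one, since the criterion requires an inserted fibre. The arithmetic assumes independent patients with a common response probability and 30 evaluable patients. The pooling and coverage points concern interpretation only and do not invalidate the rule.

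**What to change.** **Required.**

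- Delete the comparison with chemotherapy and the statement that 16/30 indicates a true rate of 53% or more.
- Describe the null as a minimum acceptable patient-level rate of at least 12 mm necrosis, and justify it from the sponsor's earlier data on the same criterion.
- Restate the operating characteristics at n = 30. If 16/30 against 30% is kept, they are one-sided alpha 0.6%, power 56% at a true rate of 53%, and 90% power at about 63%.
- If the earlier data justify a higher null, re-derive the cut-off. At one-sided 5%, an assumed level because the plan states none for efficacy:

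| Null | Cut-off | Exact alpha | True rate for 90% power |
|---|---|---|---|
| 40% | 17/30 | 4.8% | 66% |
| 50% | 20/30 | 4.9% | 75% |
| 60% | 23/30 | 4.4% | 84% |

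Do not lower the cut-off to 14/30 by default. Against 30% it would have alpha 4.0% and power 81% at 53%. But it loosens the bar using a significance level that the plan does not state and a null that still lacks a justification.

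**Optional, as estimation only.** Report the response rate with exact CIs separately for the 10 single-position and 20 multi-position patients, because the criterion refers to the only position in the first group and to any of several in the second. Report the percentage of tumour volume necrosed from the CTs already planned.

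**Cost.** The chemotherapy comparison is lost and the stated power is less favourable. A higher null would demand a higher true rate for the same power. Subgroup intervals will be wide: 5/10 has a 95% CI of 19% to 81%, and 10/20 has 27% to 73%. No extra patients or scans are needed.
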